6.0 Agent Formulation and Procurement

Dose Preparation and Storage of azacitidine (VIDAZA): Azacitidine is commercially available and will not be provided for the study by Celgene. Standard procedures should be used for preparation and administration of azacitidine. The following guidelines are suggested:

VIDAZA is a cytotoxic drug and, as with other potentially toxic compounds, caution should be exercised when handling and preparing VIDAZA suspensions. (See Handling and Disposal.)

If reconstituted VIDAZA comes into contact with the skin, immediately and thoroughly wash with soap and water. If it comes into contact with mucous membranes, flush thoroughly with water.

The VIDAZA vial is single-use and does not contain any preservatives. Unused portions of each vial should be discarded properly. See **Handling and Disposal**. Do not save any unused portions for later administration.

Preparation for Subcutaneous Administration: VIDAZA should be reconstituted aseptically with 4 mL sterile water for injection. The diluent should be injected slowly into the vial. Vigorously shake or roll the vial until a uniform suspension is achieved. The suspension will be cloudy. The resulting suspension will contain azacitidine 25 mg/mL.

Preparation for Immediate Subcutaneous Administration: Doses greater than 4 mL should be divided equally into at least 2 syringes. The product may be held at room temperature for up to 1 hour, but must be administered within 1 hour after reconstitution.

Preparation for Delayed Subcutaneous Administration: The reconstituted product may be kept in the vial or drawn into a syringe. Doses greater than 4 mL should be divided equally into at least 2 syringes. The product must be refrigerated immediately, and may be held under refrigerated conditions (2°C–8°C, 36°F–46°F) for up to 8 hours. After removal from refrigerated conditions, the suspension may be allowed to equilibrate to room temperature for up to 30 minutes prior to administration.

Subcutaneous Administration: To provide a homogeneous suspension, the contents of the syringe must be re-suspended by inverting the syringe 2–3 times and vigorously rolling the syringe between the palms for approximately 30 seconds immediately prior to administration. VIDAZA suspension is administered subcutaneously. Doses greater than 4 mL should be divided equally into 2 syringes and injected into 2 separate sites. Rotate sites for each injection (thigh, abdomen, or upper arm). New injections should be given at least 1 inch from an old site and never into areas where the site is tender, bruised, red, or hard.

Suspension Stability: Azacitidine reconstituted for subcutaneous administration may be stored for up to 1 hour at 25°C (77°F) or for up to 8 hours between 2°C and 8°C (36°F and 46°F).

Preparation for Intravenous Administration: Reconstitute the appropriate number of VIDAZA vials to achieve the desired dose. Reconstitute each vial with 10 mL sterile water for injection. Vigorously shake or roll the vial until all solids are dissolved. The resulting solution will contain azacitidine 10mg/mL. The solution should be clear. Parenteral drug product should be inspected visually for particulate matter and discoloration prior to administration, whenever solution and container permit. Withdraw the required amount of VIDAZA solution to deliver the desired dose and inject into a 50-100 mL infusion bag of either 0.9% Sodium Chloride Injection or Lactated Ringer's Injection.

Intravenous Solution Incompatibility: VIDAZA is incompatible with 5% Dextrose solutions, Hespan, or solutions that contain bicarbonate. These solutions have the potential to increase the rate of degradation of VIDAZA and should therefore be avoided.

Intravenous Administration: VIDAZA solution is administered intravenously. Administer the total dose over a period of 10-40 minutes. The administration must be completed within 1 hour of reconstitution of the VIDAZA vial.

Solution Stability: VIDAZA reconstituted for intravenous administration may be stored at 25°C (77°F), but administration must be completed within 1 hour of reconstitution.

Storage: Store un-reconstituted vials at 25° C (77° F); excursions permitted to 15°-30° C (59°-86° F) (See USP Controlled Room Temperature). There is no need to protect azacididine from exposure to light.

Handling and Disposal: Procedures for proper handling and disposal of anticancer drugs should be applied.

Sorafenib is supplied as an immediate-release film-coated, round, and salmon color tablet containing 200 mg of the free base, Sorafenib, and the excipient croscarmellose sodium, microcrystalline cellulose, hydroxypropyl methylcellulose, sodium lauryl sulfate, and magnesium stearate. The film-coat consists of hydroxypropyl methylcellulose, polyethylene glycol, titanium dioxide and red iron oxide. The film coating has no effect on the rate of release of the active sorafenib.

Sorafenib 200 mg tablets are supplied in bottles of 120 tablets. Sorafenib is Commercially available.

Taken twice daily without food (at least 1 hour before or 2 hours after a meal)

Storage

Store at 25°C (77°F): excursions permitted to 15° - 30°C (59° - 86°F) (see USP controlled room temperature). Store in a dry place.

7.0 Correlative/Special studies

These studies are not mandatory for every patient and will be done when possible.

Molecular testing for cytogenetics, FLT3 and NPM1 will be performed on all bone marrow samples obtained during the study (unless normal at baseline or thought to not be needed by the treating physician).

Whenever feasible and through the MDACC Moonshot bone marrow procurement protocol, we will attempt to submit all patients' initial, pre-treatment bone marrow specimens as well as any follow-up specimens to the Cancer Genomics Laboratory (directed by [name]) for comprehensive genomic evaluation to discern patterns of genomic evolution in responders versus non-responders.

Peripheral blood for correlative studies days (+/- 3 days) on days 0, 2, 7, 21 and 28 of the first cycle (done at MD Anderson, for [name] laboratory) will be optional. On subsequent courses samples will be obtained on day 0 (pretreatment), and day 7. All these samples can be obtained +/- 3 days. Peripheral blood samples for correlative studies (Plasma inhibitory assay and FLT3 ligand levels done at Johns Hopkins) will also be performed on days 0, 7 and 28 of the first course as well as days 0 and 7 of subsequent courses. Every effort will be made to collect these optional specimens – but any missed time point will not be considered a

deviation. Samples will be sent to: [[name] MD PhD, Professor of Oncology, Johns Hopkins Medical Institutes, [name].](#)

8.0 Patient evaluation

8.1 Pre-treatment evaluation:

- All pretreatment studies should be obtained within 14 days of entry into the trial (except bone marrow that should be done within 28 days or 14 days if patient has received medication for their disease within that period of time).
- A complete history and physical, documentation of all measurable disease, and performance status should be performed within 48 hours before initiation of study.
 - CBC, platelet count, differential (differential can be omitted if WBC is $\leq 0.5 \times 10^9/L$)
 - Creatinine, total bilirubin, ALT or AST, electrolytes and chemistry, PT, PTT, INR, Pregnancy test (urine or serum) in females, should be performed 48 hours before initiation of study unless 12 months menopausal or surgically sterilized.
 - Bone marrow aspirate during the last 28 days preceding study initiation unless patient has received medication for their disease within that period of time. Cytogenetics and Molecular studies (FLT3 and NPM1) will be obtained prior to therapy (results from prior analysis can be used for this purpose). . Molecular studies (FLT3 and NPM1) performed at baseline only and on patients with unknown status.
 - Pretreatment optional correlative studies (see 8.2.5 below)

8.2 Evaluation during treatment:

- Physical exam at the start of each cycle (± 4 days) for the first 24 cycles, then every 2-3 cycles.
- CBC, platelet count, differential once weekly for the first 2 cycles, then monthly (differential can be omitted if WBC is $\leq 0.5 \times 10^9/L$)
- Creatinine, total bilirubin, ALT or AST, electrolytes and chemistry, weekly for the first 2 cycles, then monthly. PT, PTT, INR if greater than 1.5 at baseline if clinically indicated
- Bone marrow aspiration on Cycle 1 Day 28 (+/- 4 days), every 2-3 cycles for the first two years, and then at the discretion of the treating physician.
- Peripheral blood for correlative studies days (+/- 3 days) on days 0, 2, 7, 21 and 28 of the first course (done at MD Anderson) will be optional. On subsequent courses samples will

be obtained on day 0 (pretreatment), and day 7. All these samples can be obtained +/- 3 days-

9.0 Criteria for response

Criteria for response will be as per the international working group for MDS and AML.

9.1 Response criteria for MDS: Response criteria will be according to the International Working Group (Blood 2006; 108: 419-425). Responders are patients who obtain a CR, CRi, or PR, with or without cytogenetic response, hematologic improvements, and morphologic leukemia-free state. Briefly, criteria are as follows:

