1.0 Objectives

1.1 Primary objectives:

1. To determine the clinical activity (CR +CRi) of the combination of AZA and sorafenib in patients with untreated acute myeloid leukemia and High risk MDS with FLT3-ITD mutation.

1.2 Secondary objectives:

1. To determine the toxicity profile of the combination of AZA and sorafenib in patients with untreated acute myeloid leukemias and MDS with FLT3-ITD mutation.
2. To determine potential mechanisms of synergy with this combination and its correlation with response.

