3.0 Patient selection

3.1 Inclusion criteria:

1. Patients with untreated AML ($\geq 20\%$ blasts in bone marrow and/or peripheral blood) or high risk MDS ($\geq 10\%$ blasts in bone marrow) Patients with AML and history of MDS who have received prior therapy with a hypomethylating agent (including azacitidine) and/or with lenalidomide for prior MDS are eligible if the treating physician feels that participation in the study is in the patients' best interest. Patients should have molecular evidence of the presence of FLT3-ITD mutation with a molecular burden of at least 10%.
2. Age ≥ 60 years; patients younger than 60 who are unsuitable for or unwilling to receive standard cytotoxic chemotherapy are also eligible to be enrolled.
3. ECOG Performance Status ≤ 2
4. Adequate liver (bilirubin $\leq 1.5 \times$ ULN, ALT or AST $\leq 2.5 \times$ ULN and Alkaline phosphatase $\leq 4 \times$ ULN if not related to leukemic disease) and renal (creatinine $\leq 1.5 \times$ ULN) function.
5. Patients must provide written informed consent.
6. Patients must have been off therapy for MDS for 2 weeks prior to entering this study, and must have recovered from the toxic effects of that therapy to at least grade 1, unless there is evidence of rapidly progressive disease. Use of hydroxyurea (any dose) or ara-C (up to 1 g/m² x 2 doses) for patients with rapidly proliferative disease is allowed before the start of

study therapy; these should be stopped for 24 hours prior to the initiation of azacitidine and sorafenib.

7. Women of childbearing potential should be advised to avoid becoming pregnant with an adequate method of contraception (barrier or hormonal methods) and men should be advised to not father a child while receiving treatment with azacitidine. All men and women of childbearing potential must use acceptable methods of birth control throughout the study as described below: Women of childbearing potential must have a negative serum pregnancy test performed within 7 days prior to the start of treatment. Men should use adequate birth control for at least 30 days after the last administration of sorafenib. Post-menopausal women (defined as no menses for at least one year) and surgically sterilized women are not required to undergo a pregnancy test

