9.1.1 Morphologic Complete Response (CR)

- ◆ **Peripheral blood counts:**
 - No circulating blasts
 - Neutrophil count $>1.0 \times 10^9/L$
 - Platelet count $>100 \times 10^9/L$
- ◆ **Bone marrow aspirate and biopsy:**
 - $< 5\%$ blasts
 - No extramedullary leukemia

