9.1.3 Marrow CR

- ◆ Bone marrow: $\leq 5\%$ myeloblasts and decrease by $\geq 50\%$ over pretreatment
- ◆ Peripheral blood: if HI responses, they will be noted in addition to marrow CR

9.1.4 Hematologic Improvement (HI): Hematologic response must be described by the number of positively affected cell lines.

- ◆ **Erythroid response (E)** (pretreatment Hgb <11 g/dL)
 - Hgb increase by ≥ 1.5 g/dL
- ◆ **Platelet response (P)** (pretreatment platelets $<100 \times 10^9/L$)
 - Absolute increase of $\geq 30 \times 10^9/L$ for patients starting with $> 20 \times 10^9/L$ platelets
 - Increase from $< 20 \times 10^9/L$ to $> 20 \times 10^9/L$ and by at least 100%

- ◆ **Neutrophil response (N)** (pretreatment ANC <1.0 x10⁹/L)
At least 100% increase and an absolute increase > 0.5 x 10⁹/L

9.2 Response criteria for AML: Response criteria will be modified from the International Working Group for AML (JCO 2003; 21: 4642-9). Responders are patients who obtain a CR, CRi, or PR, with or without cytogenetic response, hematologic improvements, and morphologic leukemia-free state. Briefly, criteria are as follows:

9.2.1 Complete remission (CR):

- ◆ **Peripheral blood counts:**
No circulating blasts
Neutrophil count ≥1.0 x10⁹/L
Platelet count ≥100 x10⁹/L
- ◆ **Bone marrow aspirate and biopsy:**
< 5% blasts
No Auer rods
No extramedullary leukemia

9.2.2 Complete remission with incomplete blood count recovery (CRi):

- ◆ **Peripheral blood counts:**
No circulating blasts
Neutrophil count <1.0 x10⁹/L, or
Platelet count <100 x10⁹/L
- ◆ **Bone marrow aspirate and biopsy:**
< 5% blasts
No Auer rods
No extramedullary leukemia

9.2.3 Partial remission:

All CR criteria if abnormal before treatment except:
≥50 % reduction in bone marrow blast but still >5%

- ◆ **Morphologic leukemia-free state:**
Bone marrow: ≤5% myeloblasts

9.2.4 Hematologic Improvement (HI): Hematologic response must be described by the number of positively affected cell lines.

- ◆ **Erythroid response (E)** (pretreatment Hgb <11 g/dL)
Hgb increase by ≥1.5 g/dL

- ◆ **Platelet response (P)** (pretreatment platelets $<100 \times 10^9/L$)
 - Absolute increase of $\geq 30 \times 10^9/L$ for patients starting with $> 20 \times 10^9/L$ platelets
 - Increase from $< 20 \times 10^9/L$ to $> 20 \times 10^9/L$ and by at least 100%
- ◆ **Neutrophil response (N)** (pretreatment ANC $<1.0 \times 10^9/L$)
 - At least 100% increase and an absolute increase $> 0.5 \times 10^9/L$

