13.1 Efficacy

The primary endpoint is the overall response (CR+CRi) after three cycles of treatment. The historical data suggested the overall response rate is 45%. With the assumption that the improved overall response rate to be 65%, it is estimated that a total of 52 evaluable patients will yield 83% power at a significance level of 5% based on chi-square test. The trial will be continuously monitored. The study will be stopped early if the data suggest that:

$$\Pr(\pi > 0.45 | \text{data}) < 0.05$$

Here π is the overall response (OR) rate. That is, if at any time during the study we determine that there is a less than 5% chance that the average OR rate is greater than 45%, we will terminate the study. The OR rate is assumed to follow a non-informative prior of Beta (0.9, 1.1).

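### Does the missing CRi definition in the MDS response criteria leave the CR+CRi primary endpoint open for MDS patients?

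*Combined protocol and SAP*

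**What the plan says.** Section 1.1 gives the primary objective as "To determine the clinical activity (CR +CRi) of the combination of AZA and sorafenib" in untreated AML and high-risk MDS with FLT3-ITD. Section 13.1 repeats the endpoint without splitting it by disease: "The primary endpoint is the overall response (CR+CRi) after three cycles of treatment". Section 3.1 admits MDS patients from 10% marrow blasts upward and gives no planned number or cap for them.

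Section 9 has two sets of criteria, 9.1 for MDS and 9.2 for AML. Each opens with the same sentence: "Responders are patients who obtain a CR, CRi, or PR, with or without cytogenetic response, hematologic improvements, and morphologic leukemia-free state". Each list is introduced as a brief summary of a cited publication.

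- Under 9.1 the itemised classes are CR, PR, marrow CR and hematologic improvement. CR (9.1.1) needs fewer than 5% blasts and recovery of both neutrophils and platelets. Marrow CR (9.1.3) reads "Bone marrow: $\leq 5\%$ myeloblasts and decrease by $\geq 50\%$ over pretreatment" and sets no count threshold.
- Under 9.2, CRi (9.2.2) needs fewer than 5% blasts, no circulating blasts, no Auer rods and no extramedullary leukemia, with at least one count still low: "Neutrophil count <1.0 x10⁹/L, or" platelets below 100 x 10⁹/L.

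No sentence links marrow CR to CRi or says that 9.2.2 also serves MDS.

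**The concern.** CRi is half of the primary endpoint, and in the section written for MDS it is named but not defined. Take an MDS patient whose blasts clear while counts stay low. The printed MDS list offers the label marrow CR, which does not appear in CR+CRi. The AML list offers CRi, which does. A scorer who kept strictly to the 9.1 list could record a failure where another recorded a success.

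The endpoint would then also differ by disease. In AML, 9.2.1 and 9.2.2 together accept blast clearance with or without count recovery. In MDS, only responses with both counts recovered would be left. This is a single-arm trial with response looks every four patients, so a scoring choice made late could affect both the final count and the comparison with the futility boundaries in Table 13.1.

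**Working it through.** **Step 1: who meets marrow CR.** An eligible MDS patient starts at b% blasts with b ≥ 10 (section 3.1). A fall to 5% is a relative fall of (b − 5)/b = 1 − 5/b. At b = 10 this is 1 − 0.5 = 50%, and it is larger for any higher b. The second condition of 9.1.3 is therefore met whenever the first is. Every MDS patient who reaches 5% blasts or fewer is a marrow CR, whatever the counts.

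**Step 2: what that implies.** A patient in CR under 9.1.1 has fewer than 5% blasts, so that patient also meets 9.1.3. If meeting 9.1.3 put a patient outside CR+CRi, every MDS complete responder would be outside it too, and no reader would accept that. The classes in 9.1 overlap; they are not exclusive bins. The AML list has the same overlap: a CRi under 9.2.2 also satisfies the morphologic leukemia-free state (5% myeloblasts or fewer), yet plainly counts as CRi. So the marrow CR label settles nothing, and the question is only what CRi means for MDS.

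**Step 3: the possible readings against the text.**

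| Reading for MDS | 1.1 and 13.1 (CR+CRi, both diseases) | 9.1 (names CRi) | Printed definition |
|---|---|---|---|
| CRi is scored by 9.2.2 | fits | fits | the only one there is |
| CRi cannot occur in MDS | leaves half the endpoint empty for MDS | contradicts it | none needed |
| Every marrow CR is a CRi | fits | fits | none; 9.1.3 admits exactly 5% blasts and omits the bars on circulating blasts, Auer rods and extramedullary leukemia |

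Only the first agrees with all the text. A patient who meets 9.2.2 is then a CRi, and a marrow CR that meets neither 9.1.1 nor 9.2.2 is a descriptive category outside the primary endpoint. One seam remains: 9.1.1 requires counts strictly above 1.0 and 100, while 9.2.2 requires one strictly below, so a count exactly on a threshold with the other not low is in neither class. A scorer settles such a tie without consequence.

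**Step 4: the plan's own figures.** Inputs from 13.1 are n = 52, 45% against 65%, and 5% significance; sidedness is not stated. A two-sided one-sample chi-square test gives

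z = [√52 × 0.20 − 1.96 × √(0.45 × 0.55)] / √(0.65 × 0.35) = (1.442 − 0.975)/0.477 = 0.979, so power is 83.6%.

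The matching rejection region is 31 or more of 52, with exact power 83.2% and upper-tail error 2.4%. The stated 83% reproduces. Recomputing the futility rule with the Beta(0.9, 1.1) prior and the 45% threshold gives all 12 rows of the response column in Table 13.1. None of these calculations uses the MDS criteria, so none changes with the reading.

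**The case for a change.** The strongest reply is that the headings assign 9.1 to MDS and 9.2 to AML, so carrying 9.2.2 into MDS is an inference, and a primary endpoint should not rest on inference. CRi is not a rare class either: in the earlier trial of this combination in AML, 16 of the 24 CR or CRi responses were CRi. As an illustration, suppose 1, 2 or 3 MDS patients were moved out of CR+CRi at a true rate of 65%. With X ~ Bin(52, 0.65), the chance that a count of 31 or more falls below 31 is P(31 ≤ X ≤ 30 + k) = 8.1%, 18.0% or 29.1%.

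What stands is that 9.1 names CRi without a definition or a cross-reference. The headings do not settle that, because following 9.1 strictly leads to a term it never defines.

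The probabilities carry little weight. The number of affected patients is assumed; the documents give no MDS share, and with no MDS patients the effect is zero. The 31/52 cut-off is derived from the power statement, whereas 13.3 plans response rates with 95% confidence intervals. The calculation also presumes the reading that contradicts 9.1. Finally, 9.1 defers to a cited publication that was not available here, so it cannot be said that nothing fixes the choice in advance.

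The mention of PR in the responder sentence adds no ambiguity: 13.1 restricts overall response to CR+CRi, and Table 13.1 uses that term.

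**Conclusion.** The omission is real but it is missing detail, not a fault in the design or analysis. The objectives, the responder sentence in 9.1 and the single printed CRi definition point to scoring MDS patients by 9.2.2, which is what an analyst would do. On that reading the primary endpoint is determined for MDS patients, apart from a count lying exactly on a threshold, and no result changes. The sample size, power and stopping boundaries are unaffected under any reading. The conclusion assumes that scorers treat the 9.1 classes as overlapping, as Step 2 shows they must, and that the cited MDS publication does not direct otherwise, which could not be checked. The size of any effect under a different reading cannot be derived, because the number of MDS patients who clear blasts with low counts is not in the documents and may be zero. No change to the plan is called for.

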9.1.1 Morphologic Complete Response (CR)

- ◆ **Peripheral blood counts:**
 - No circulating blasts
 - Neutrophil count $>1.0 \times 10^9/L$
 - Platelet count $>100 \times 10^9/L$
- ◆ **Bone marrow aspirate and biopsy:**
 - $< 5\%$ blasts
 - No extramedullary leukemia

9.1.2 Partial Response (PR)

- ◆ All CR criteria if abnormal before treatment except:
- ◆ $\geq 50\%$ reduction in bone marrow blast but still $>5\%$

9.1.3 Marrow CR

- ◆ Bone marrow: $\leq 5\%$ myeloblasts and decrease by $\geq 50\%$ over pretreatment
- ◆ Peripheral blood: if HI responses, they will be noted in addition to marrow CR

9.1.4 Hematologic Improvement (HI): Hematologic response must be described by the number of positively affected cell lines.

- ◆ **Erythroid response (E)** (pretreatment Hgb <11 g/dL)
 - Hgb increase by ≥ 1.5 g/dL
- ◆ **Platelet response (P)** (pretreatment platelets $<100 \times 10^9/L$)
 - Absolute increase of $\geq 30 \times 10^9/L$ for patients starting with $> 20 \times 10^9/L$ platelets
 - Increase from $< 20 \times 10^9/L$ to $> 20 \times 10^9/L$ and by at least 100%

- ◆ **Neutrophil response (N)** (pretreatment ANC <1.0 x10⁹/L)
At least 100% increase and an absolute increase > 0.5 x 10⁹/L

9.2 Response criteria for AML: Response criteria will be modified from the International Working Group for AML (JCO 2003; 21: 4642-9). Responders are patients who obtain a CR, CRi, or PR, with or without cytogenetic response, hematologic improvements, and morphologic leukemia-free state. Briefly, criteria are as follows:

9.2.1 Complete remission (CR):

- ◆ **Peripheral blood counts:**
No circulating blasts
Neutrophil count ≥1.0 x10⁹/L
Platelet count ≥100 x10⁹/L
- ◆ **Bone marrow aspirate and biopsy:**
< 5% blasts
No Auer rods
No extramedullary leukemia

9.2.2 Complete remission with incomplete blood count recovery (CRi):

- ◆ **Peripheral blood counts:**
No circulating blasts
Neutrophil count <1.0 x10⁹/L, or
Platelet count <100 x10⁹/L
- ◆ **Bone marrow aspirate and biopsy:**
< 5% blasts
No Auer rods
No extramedullary leukemia

9.2.3 Partial remission:

All CR criteria if abnormal before treatment except:
≥50 % reduction in bone marrow blast but still >5%

- ◆ **Morphologic leukemia-free state:**
Bone marrow: ≤5% myeloblasts

9.2.4 Hematologic Improvement (HI): Hematologic response must be described by the number of positively affected cell lines.

- ◆ **Erythroid response (E)** (pretreatment Hgb <11 g/dL)
Hgb increase by ≥1.5 g/dL

- ◆ **Platelet response (P)** (pretreatment platelets $<100 \times 10^9/L$)
 - Absolute increase of $\geq 30 \times 10^9/L$ for patients starting with $> 20 \times 10^9/L$ platelets
 - Increase from $< 20 \times 10^9/L$ to $> 20 \times 10^9/L$ and by at least 100%
- ◆ **Neutrophil response (N)** (pretreatment ANC $<1.0 \times 10^9/L$)
 - At least 100% increase and an absolute increase $> 0.5 \times 10^9/L$

